18.0 Potential Benefits to Subjects

18.1 Describe the potential benefits that individual subjects might experience from participating in the research. Include the probability, magnitude, and duration of the potential benefits, as this will be useful to the IRB's risk:benefit analysis. Do not include benefits to society or others. Do not list monetary or non-monetary compensation for participation, as this is not a benefit. These should be included in section 2 or 3 of this document:

Participants who receive a DEXA scan will benefit from receiving this test at no cost. It can detect osteoporosis.

Balance training participants may benefit from balance training by improving their balance. However, this has not been formally evaluated at this time.

18.2 If applicable, specify that there are no anticipated direct benefits for participants:

N/A

19.0 Data Management and Confidentiality

19.1 Describe procedures that you will use for quality control to ensure validity of collected data:

21-1072 Validation and application of wearable sensors for capturing responses to losses of balance

We have extensive experience implementing similar procedures and training in prior studies, and will leverage that experience during the planning and execution of this study. We will also adequately pilot test the protocols described here prior to enrolling any participants, including sufficient practice to ensure we are thorough and consistent with our procedures.

19.2 Describe any existing data or biospecimens you will obtain as part of this study. Include:

- *Variables or samples to be obtained*
- *Source of the data or specimens*
- *Your authorization to access or receive the data or biospecimens*
- *Whether the data or biospecimens are publicly available*
- *Whether the data or specimens you receive will contain identifiers*

Participants who have had a DEXA scan within the last year will be asked to obtain a copy of the scan results from their physician. In particular, we will review the bone mineral density of the lumbar vertebra and proximal femur. This must not be $t < -2.5$, which is an indication of clinical osteoporosis.

19.3 Describe the steps that you will take to handle and secure study data during data collection, storage, use, and transmission. Include information about training of study staff, authorization of access, password protection, encryption, physical controls, certificates of confidentiality, separation of identifiers and data, etc.:

Any paper-based records will be kept in our restricted-access research lab or the PI's office, and only be accessible to personnel involved in the study.

Data computer files will be de-identified (will only use participant numbers) and be maintained on password-protected computers/networks or students investigator's personal computers. If the latter, it will be required that they meet Virginia Tech security requirements for low risk data described here: <https://security.vt.edu/resources.html>. Personally-identifiable data (name, email, and phone number for corresponding with participants) will only be stored on password-protected computers managed and secured by Virginia Tech.

De-identified data to be used for Phase 2 of the screening process and data analysis will be shared with external collaborators using a VT Google Drive with access limited to recipients.

21-1072 Validation and application of wearable sensors for capturing responses to losses of balance

For DEXA scanning, the study team will use pseudonyms (subject numbers) rather than identifiable information. The results from this test will be a hard-copy print out provided to the investigator. These data will not be transmitted via email.

19.4 For multi-site studies, describe how data or specimens will be handled and secured for each site (e.g., central or disseminated data storage, data coordinating center):

N/A

19.5 Describe the plan for data disposition following the conclusion of the study (e.g., long term maintenance of data, data destruction methods).

- *What information will be included in the long term storage of data or specimens?*
- *How long will the data or specimens be stored?*
- *Where and how data or specimens will be stored?*
- *Who will have access to the data or specimens during long term storage?*
- *Who is responsible for receipt or transmission of the data or specimens?*
- *How will data or specimens be shared or transported?*
- *When and how will personal identifiers be destroyed?*

We will keep data for the foreseeable future for potential use in subsequent studies, presentations, and pilot data for proposals. Paper-based records will be kept in a secured location only accessible to the principal investigator. Computer-based files will be password protected and only available to personnel involved in the study. Personal identifiers will be destroyed one year after the completion of the study by deleting these files and ensuring they are completely removed from paper-based records and the computer.

20.0 Provisions to Protect the Privacy Interests of Subjects

20.1 Describe the steps that you will take to protect subjects' privacy interests. "Privacy interest" refers to a person's desire to place limits on with whom they interact or to whom they provide personal information (e.g., collecting the minimal amount of private information required to complete the study, protecting the data once it is obtained):

Personal data over the phone will only be obtained for scheduling purposes, and will not be shared with anyone outside of the research group. All other data will be collected

21-1072 Validation and application of wearable sensors for capturing responses to losses of balance

in a private room for performing research interventions. Interviews and data collection will only be administered by research personnel involved in the project.

Participants will also be provided access to a nearby restroom to change into appropriate attire for their balance testing session.

20.2 Describe steps that you will take to make subjects feel at ease with the research situation in terms of the questions being asked and the procedures being performed. “At ease” does not refer to physical discomfort, but the sense of intrusiveness a subject might experience in response to questions, examinations, and procedures (e.g., use of a same gender investigator to place sensors on the torso, a private changing area if clothing must be changed, sensitivity when discussing pregnancy testing with subjects, making it clear on surveys that participants can discontinue at any time, not asking questions about private or sensitive issues unless necessary for the research):

We will make it clear that participants can discontinue their participation without penalty. We will ask participants how they are doing and feeling throughout testing, and give plenty of encouragement. We will keep them well-informed throughout each session so they are aware of what is going on and what to expect.

When possible, sensors will be fit and applied by a member of the study team that is the same sex as the participant.

We will also develop an illustrated step-by-step instructional packet on the wearable sensors usage for participants to use at home.

20.3 Describe how you plan to access existing sources of information about the subjects (e.g., medical records, grades) and how you will protect participant privacy through the data security plan:

If a participant opts to use the results of a DEXA scan they had within the last 12 months, rather than having a new scan performed for this study, will be asked to obtain a copy of this prior scan from their physician.

20.4 Describe any required reporting that might occur as a result of your research questions, study populations, and data collection methods. Examples for Virginia and Virginia Tech include:

- Any suspicions (e.g., circumstantial, disclosed) of child abuse (physical, emotional, sexual) and neglect
- Sexual discrimination and/or sexual violence that involves a student

21-1072 Validation and application of wearable sensors for capturing responses to losses of balance

- *Disclosure or signs of intention to harm oneself (i.e., suicidal ideation and/or plan)*
- *Disclosure or signs of desire to harm others (i.e., homicidal ideation and/or plan)*
- *Suspected abuse, neglect or exploitation of vulnerable adults (e.g., individuals with a disability, elderly persons)*

N/A

21.0 Provisions to Monitor the Data to Ensure the Safety of Subjects

Safety monitoring is required when research involves greater than minimal risk and is sometimes appropriate for other studies.

21.1 Describe:

- *The plan to periodically evaluate the data collected regarding both harms and benefits to determine whether subjects remain safe (e.g., periodic reporting to the IRB, establishing a data monitoring committee, reporting data monitoring committee findings to the IRB and the sponsor).*
- *What data you will review, including safety data, unexpected events, and data that show the ability to produce the intended results.*
- *How the safety information will be collected (e.g., with case report forms, at study visits, by telephone calls with subjects).*
- *The frequency of data collection, including when safety data collection starts.*
- *Who will review the safety data and with what frequency.*
- *The statistical tests for analyzing the safety data to determine whether harm is occurring.*
- *Any conditions that will trigger an immediate suspension of the research (e.g., a serious adverse event).*

The only potential safety-related concerns will occur during the experimental sessions and balance training sessions with the participants. We will use the strategies described above to minimize these risks, and keep in constant communication with the participant during experimental sessions regarding testing protocol and any potential risk.

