4.0 Study Endpoints

4.1 *Describe the primary and secondary **study** endpoints. See links below for discussion of study endpoints and how they may differ from study objectives. These are most common in clinical trials but are sometimes applicable to other types of biomedical research, as well as social, behavioral, or educational research. See link below for a discussion.*

https://docs.google.com/document/d/1Wocz7K7a0hCQJPO_khh511SOQjhGDDGHzcOPRHR5Tw/edit?usp=sharing

Study endpoints for all participants will include:

- 1) measurements of body movements during responses to LOBs after lab-induced trips and slips
- 2) two or three weeks of using wearable sensors to measure body movements during responses to LOBs after naturally-occurring trips and slips during daily life
- 3) during the two or three weeks of using wearable sensors, participants will also use a digital voice recorder to record a description of the context of each real-world LOB. Specifically, participants will be asked to make a short recording

21-1072 Validation and application of wearable sensors for capturing responses to losses of balance

after each LOB to describe (1) what they were doing at the time (e.g., “I was walking across my living room”), (2) how they lost their balance (e.g., “I tripped over my dog”), (3) why they lost their balance (e.g., “my dog ran in front of me to bark at the mailman”), and (4) the results of LOB (e.g., “I fell, or did not fall, as a result”).

4.2 *Describe any primary or secondary safety endpoints. These should be included for all studies that are greater than minimal risk. (Minimal risk: The probability and magnitude of harm or discomfort anticipated in the research that are not greater in and of themselves than those ordinarily encountered in daily life or during the performance of routine physical or psychological examinations or tests.):*

No safety endpoint is included while using wearable sensors in the real-world during daily life because the use of the wearable sensors does not increase risk above that normally experienced during every day life.

During balance training (among balance training participants), safety endpoints will include number of times the spotter is needed to provide support to the participant during training, and the number of times the participant is fully supported by the harness during measurements of responses to lab-induced LOBs.

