- f) the same balance testing methodology employed here has been used in several of our prior studies without adverse outcome;

21-1072 Validation and application of wearable sensors for capturing responses to losses of balance

- g) an investigator and a spotter will be nearby participants to provide balance assistance, if necessary during balance training; and
- h) participants will wear a safety harness to prevent a fall to the floor during balance testing. The PI (who has extensive experience using the harnesses) will train the relevant study team member(s) in selecting the proper size safety harness, appropriately tightening all safety harness straps and connections, and setting the proper length of the lanyard that connects the harness to the overhead support. The harnesses we will be using are rated for individuals up to 310 lb, and we will limit our recruitment to individuals up to 250 lb.

No safeguards will be used during the two or three weeks of wearable sensor use since this phase of the study does not involve risk greater than that experienced during daily life.

All devices used in this study (lab-based motion capture system, wearable sensors, and voice recorders) will be used in the same manner as their approved use. Also, the use of these sensors does not influence behavior and therefore does not affect risk.

8.4 What data will you collect during the study and how you will obtain them? Please include descriptions of electronic data collection, database matching, and app-based data collection:

Participant anthropometric and demographic information will be collected and recorded in a computer file on a password-protected and VT-managed computer. In this file, participants will only be identified by a numeric code, and not personally-identifiable information will be recorded.

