Data collected during the laboratory testing session will include body motion during trip and slip LOB responses obtained simultaneously from two systems. The first system is the wearable sensors (<https://apdm.com/wearable-sensors/>) with individual sensors worn on each foot and one on the sternum using a shoulder strap under the clothing. The second system is the lab-based optoelectronic motion capture system (Qualisys, Inc) and reflective markers (small balls approximately 1 cm in diameter) placed at specific locations on the body. Data from these systems will be recorded as a computer file on a password-protected and VT-managed computer. In these files, participants will only be identified by a numeric code, and not personally-identifiable information will be recorded.

Video recordings and photographs of participants during perturbations will be obtained to assist with data analysis and for possible use in presentations. Participants will need to provide permission, on the Informed Consent Form, for us to use these in presentations. These videos and photos will be kept on a password-protected and VT-managed computer.

Data from the wearable sensors during real-world LOB response tracking will be automatically stored onboard the sensors themselves until downloaded by the study

21-1072 Validation and application of wearable sensors for capturing responses to losses of balance

team when returned to the study team after the two or three week data collection. Participants will be asked to charge the sensors nightly, and will be given the charger and detailed instructions and training on how to do that from the study team. When downloaded by the study team, the data file is in the form of a de-identified Excel file that is ready for analysis, and these files will be kept on a password-protected and VT-managed computer.

Data will be collected by the voice recorder by having participants press a record button on it, having participants speak into the recorder the information requested by the study team, and then pressing a button to stop. These recordings include a time/date stamp, and will be downloaded for analysis by the study team when returned to the study team. These files will be kept on a password-protected and VT-managed computer.

8.5 Who will transcribe or code audio and/or video recordings?:

[name] will transcribe voice recordings. No other transcriptions will be performed.

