17.0 Risks to Subjects

17.1 List the reasonably foreseeable risks, discomforts, hazards, or inconveniences to the subjects related to the subjects' participation in the research. Include for the IRB's consideration a description of the probability, magnitude, duration, and reversibility of the risks. Consider physical, psychological, social, legal, privacy, and economic risks. Do not indicate "No risk" or "N/A." Instead, for studies with very low risk (e.g., anonymous online questionnaire on a mundane topic) indicate "The investigators are not aware of any risks from participation in this study." or "No more than risks than are found in everyday life." The example consent form presents a tabular method for risk information, which you can also use here. Common risk types include:

- *Physical (e.g., potential for pain, discomfort, infection)*
- *Psychological (e.g., potential for stress, discomfort, and/or embarrassment)*
- *Social (e.g., potential for discrimination or stigmatization and disruption of personal and family relationships)*
- *Legal (e.g., potential for disclosure of illegal activity, negligence)*
- *Privacy (e.g., potential for personal information being accessed, used, or disclosed without the subjects' knowledge or consent, breach of confidentiality/security)*
- *Economic (e.g., potential for individuals to lose access to economic services, employment, insurability)*

21-1072 Validation and application of wearable sensors for capturing responses to losses of balance

There are potential risks for participants in the proposed work.

1. During a DEXA scan, participants will be exposed radiation. The amount of radiation is less than 2 days' exposure to natural background radiation (NBR). By comparison, a chest X-ray uses the equivalent of about 3 days' exposure to NBR, and a flight from UK to USA is equivalent to approximately a week's exposure to NBR (<https://www.nhs.uk/conditions/dexa-scan/#:~:text=The%20amount%20of%20radiation%20used,a%20week's%20exposure%20to%20NBR>).
2. During balance training or testing, there is a risk of muscle strains, joint strains, other soft tissue injury, or broken bones. The risk of these outcomes is considered low given our safety measures described in 17.2.
3. During balance training or testing, there is a risk of participants overexerting themselves. This risk is considered low given our safety measures described in 17.2.

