4. During balance testing, the physical risk of skin irritation and bacterial exposure related to the reflective markers, lab-provided rubber soled shoes and clothing, as well as the safety harness, are very low (but not zero). We are not aware of a single incident of this in the PI's 20 years of conducting human subjects research.
5. After balance training or testing, there is the potential for participants to experience muscle or joint soreness. This risk is no different than participation in physical exercise, and is mitigated by the safety measures described in 17.2.
6. During the two-weeks of using wearable sensors, there is no more risk than is found in everyday life for losses of balance or falls because these sensors do not affect balance or fall risk.
7. In the event the wearable sensors are lost, stolen, or damaged during the course of the research, participants will not be held financially responsible for their replacement.

17.2 Indicate the measures you will use to minimize risks and monitor subjects for safety. (e.g., asking a subject at regular intervals to rate how they are feeling from 1 to 10, or to slowly crouch in order to check their balance.)

To minimize the risks described above in 17.1, the following safety measures will be used:

- a) using our medical screening process to exclude individuals at an increased risk of injury;

21-1072 Validation and application of wearable sensors for capturing responses to losses of balance

- b) having subjects complete warm-up exercises prior to balance training and testing including walking on a treadmill and stretching;
- c) the balance training used here was designed to be completed by adults 65-80 years;
- d) the balance training is tailored to each participant's capabilities;
- e) rest breaks will be provided as needed by the participant
- f) the same balance testing methodology employed here has been used in several of our prior studies without adverse outcome;
- g) an investigator and a spotter will be nearby participants to provide balance assistance, if necessary during balance training; and

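### Section 17.1 names injuries and later soreness as risks, but the visible protocol describes no record or count of either, and 21.1 limits safety concerns to the sessions

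*Combined protocol and SAP*

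**What the plan says.** Section 17.1, item 2, states that during balance training or testing "there is a risk of muscle strains, joint strains, other soft tissue injury, or broken bones". Item 5 adds: "After balance training or testing, there is the potential for participants to experience muscle or joint soreness". The protocol rates the soreness itself: "This risk is no different than participation in physical exercise, and is mitigated by the safety measures described in 17.2".

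Section 21.1 answers the template's safety monitoring prompts in two sentences. The first is "The only potential safety-related concerns will occur during the experimental sessions and balance training sessions with the participants". The second promises to use the risk-reduction measures already described and to "keep in constant communication with the participant during experimental sessions regarding testing protocol and any potential risk".

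Section 4.2 states that "safety endpoints will include number of times the spotter is needed to provide support to the participant during training", together with the number of times the harness fully supports the participant in the laboratory perturbation tests. It sets no safety endpoint for the sensor period.

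Section 8.4 lists the data to be collected. It begins "Participant anthropometric and demographic information will be collected and recorded in a computer file" and continues "Data collected during the laboratory testing session will include body motion during trip and slip LOB responses obtained simultaneously from two systems". Video and photographs, real-world sensor files and voice recordings follow.

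Three contacts could bring a complaint to light: a general question during testing (20.2), a weekly question about how participants are getting on (24.1), and calls on days 1 and 3 of sensor use to solve sensor problems (8.2).

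**The concern.** The protocol names the harms that it expects might occur, then describes no place where they would be written down. Spotter and harness counts show how often help was given. They do not show whether anyone was hurt. The 21.1 template asks how safety information is collected, how often, who reviews it, how it is analysed and what would suspend the study. The answer supplies none of these, and 5.2 has no safety analysis.

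At stake is the study's ability to report harms for three training programmes in adults aged 65 to 80. One of the programmes (NT) is put forward as a cheaper alternative to treadmill training, so a reader will want to know what happened to the people who did it. A second, smaller stake is safety within the study. Difficulty is raised on the investigator's perception of ability (8.2), and a recorded answer before each session would give the trainer one more fact.

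**Working it through.** **Places where a harm record could stand**

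| Section | What it provides | Injury or soreness recorded? |
|---|---|---|
| 4.2 | Spotter support in training; full harness support in lab tests | No |
| 5.2 | Analyses for Hypotheses 1 to 4 | No safety analysis |
| 8.2 | Day 1 and day 3 calls | Purpose is sensor support; no record stated |
| 8.4 | Anthropometric, demographic, motion, video, sensor and voice data | No |
| 20.2 | General question during testing | No record stated |
| 21.1 | Communication during experimental sessions | No record stated |
| 24.1 | Weekly general question, under ongoing consent | No injury wording or record stated |

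**The plan's own figure.** The only computed figure is the sample size in 14.1. With d = 17.4/12 = 1.45 and one-sided alpha 0.05, the noncentral t distribution gives power of 75.5% at n = 6 and 81.9% at n = 7 per group. The stated 7 reproduces; 10 are recruited. The point does not depend on it, but it fixes the denominators below.

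**Exposure (7.1).** At most 40 perturbations × 2 sessions × 3 weeks = 240 per TT participant, and × 10 = 2,400 in the TT group. This is a ceiling, and TT participants wear a fall-protection harness.

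**What a systematic count could support.** With zero events in n participants, the one-sided 95% upper limit is 1 − 0.05^(1/n):
- n = 10: 25.9%
- n = 30: 9.5%
- n = 60: 4.9%

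**Expected counts under assumed rates (the documents give none).**
- Injury in 1% to 5% of participants: 30 × 0.01 = 0.3 to 30 × 0.05 = 1.5 expected among the trained. The chance of at least one is 1 − 0.99^30 = 26.0% to 1 − 0.95^30 = 78.5%.
- Soreness in 10% to 50%: 3 to 15 of the 30 trained.

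**Staff load of a fixed question, lab session before the sensor weeks.**
- Trained: 5 (start of sessions 2 to 6) + 1 (start of lab session) + 2 (calls) = 8; × 30 = 240 answers.
- Untrained: 2 calls × 30 = 60.
- Weekly checks in weeks with no other listed contact: trained, sensor week 2, 1 × 30 = 30; untrained, sensor weeks 2 and 3, 2 × 30 = 60. Together 90.
- Total 240 + 60 + 90 = 390 answers, or 6.5 hours at 1 minute and 13 hours at 2 minutes.
- If every weekly check is a separate contact (5 per trained, 3 per untrained): 300 + 150 + 90 = 540 answers, or 9 to 18 hours.

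**If the lab session comes last for untrained participants**, as 5.1 and 8.1 say, no session precedes their sensor weeks, so the question is needed only in one later call. Trained: 240 + 30 = 270 to 240 + 150 = 390 answers, or 4.5 to 13 hours. Adding 30 calls × 5 minutes (assumed) = 2.5 hours gives 7 to 15.5 hours, inside the same range.

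**The case against.** The strongest reply is that staff already ask. Section 24.1 commits them to a weekly question, trained participants meet the investigator one-on-one twice a week, and everyone is called on days 1 and 3 of sensor use, with daily calls possible. An injury during a one-on-one, spotted session would probably be noticed. This stands. A reader might infer that late complaints depend wholly on the participant volunteering them, and the documents do not support that. The gap is in wording, recording and counting.

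A reader might also infer that 21.1 flatly contradicts 17.1. It need not: 21.1 can be read as saying where the hazard arises, not when symptoms appear, and 17.1 openly names later soreness as an ordinary effect of exercise. The conflict is partly loose wording.

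Sections 8.3 and 17.2 say that the same testing method was used in several earlier studies with no adverse outcome. That is the only injury history in the documents and belongs beside the assumed rates above. It has no denominator and covers testing, not training, so it does not replace a record here.

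The list in 4.2 may not be complete, since it is introduced as what the endpoints will include. Data forms are uploaded separately and are not visible; one may hold such an item. Both limits are fair and keep the point to the visible text.

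Finally, holding progression for ordinary soreness could change the training dose, perhaps unequally across groups. That is a sound objection to a broad review rule, and the fix avoids it.

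**Conclusion.** The point holds in a limited form. The visible protocol names injuries and later soreness but describes no recording, no injury-specific question and no planned count by group. It should be corrected because the remedy adds useful harms data at contacts that the study already makes.

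The size of the harm is unknown. The 1% to 5% and 10% to 50% rates are assumptions that only set a scale. Nothing in the documents shows that the training is unsafe or that anyone has been hurt, and none of the planned hypothesis tests is affected. With 10 per group the counts would describe each group and could not compare NT with TT: even zero events leaves an upper limit of 25.9%. Confidence is medium, mainly because a separately uploaded form could already hold the item.

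**What to change.** 1. Reword 21.1 to cover events during and after sessions.
2. Ask and log one fixed question: *any pain, soreness, injury or medical care since your last session?* Use the start of training sessions 2 to 6, the start of the lab session for trained participants, the day 1 and day 3 calls, and the existing weekly check. Also log any injury seen in a session.
3. The principal investigator promptly reviews entries of injury or medical care only. Ordinary soreness is logged and does not hold progression.
4. In 4.2 add two descriptive counts, by group and pooled: participants with an injury or needing medical care, and participants with soreness only. Counting participants keeps repeated reports from inflating the figures.
5. Sections 5.1 and 8.1 put the lab session after the sensor weeks for untrained participants, while 6.1 and 8.2 suggest that it comes first. If it comes last, make one short call in the following week.
6. If an uploaded form already has this item, cite it in 21.1 and add only the counts.

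Cost: protocol wording, one line on the contact log, and roughly 6.5 to 18 staff hours over the study at an assumed 1 to 2 minutes per answer, plus brief review time for the principal investigator. No new visits and no change in sample size. The downside is more minor events reported, some of them daily-life pain unrelated to the sessions.
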